APPENDIX 2 SAMPLE SUBJECT DIARY

A copy of the following sample Subject Diary will be provided to the study site. The investigator must give each subject a copy of this Subject Diary at Visit 2/Baseline and all follow-up visits, as necessary.

Product Name: TDM-105795 Topical Solution
Sponsor Name: Technoderma Medicines Inc.

Protocol: 239-11651-203
Protocol Date: November 30, 2022, v1.0

PROTOCOL:	SITE:	SUBJECT NO.:	INITIALS:
239-11651-203	_____	_____	_____

SAMPLE SUBJECT DIARY

Contact the study staff at the telephone number below if you have any questions.

Contact: _____ At: _____

Please apply the study medication to the balding areas of your scalp
ONCE DAILY at approximately the same time as Day 1 application every morning.

Day 1 Application Time: _____ : _____ AM

After dosing, record the date and time of the study medication application.
If you miss a dose, write *MISSED* in the space for time.

DATE (dd/MMM/yyyy)	TIME		Full Dose Applied		If No, Explain
	12-hour clock	Circle One			
/ /	:	AM / PM	 Yes	 No	
/ /	:	AM / PM	 Yes	 No	
/ /	:	AM / PM	 Yes	 No	
/ /	:	AM / PM	 Yes	 No	
/ /	:	AM / PM	 Yes	 No	
/ /	:	AM / PM	 Yes	 No	
/ /	:	AM / PM	 Yes	 No	
/ /	:	AM / PM	 Yes	 No	
/ /	:	AM / PM	 Yes	 No	
/ /	:	AM / PM	 Yes	 No	
/ /	:	AM / PM	 Yes	 No	
/ /	:	AM / PM	 Yes	 No	
/ /	:	AM / PM	 Yes	 No	
/ /	:	AM / PM	 Yes	 No	
/ /	:	AM / PM	 Yes	 No	
/ /	:	AM / PM	 Yes	 No	
/ /	:	AM / PM	 Yes	 No	
/ /	:	AM / PM	 Yes	 No	

BACK OF SAMPLE SUBJECT DIARY

Next Appointment: _____ / _____ / _____ at _____ AM/PM
Weekday dd MMM yyyy

Site Use Only:	Diary Dispensed at:	Date Dispensed:	Date Returned:
	 Visit 2  Visit 3  Visit 4  Visit 6  Visit 8		

APPENDIX 3 INVESTIGATIONAL PRODUCT INFORMATION

A 3.1 Investigational Product Packaging and Labeling

The IP will be packaged and labeled by the Sponsor or designee. The different concentrations of TDM-105795 solution and Placebo will be packaged in identical unit dose droppers contained within labeled Subject Kits.

Each dropper of the IP within the kit will contain, at a minimum, the following information: the protocol number, kit number, the contents, storage conditions, and an investigational IP disclaimer (e.g., Caution: New Drug Limited by Federal (or United States) Law to investigational use).

Subject Kit labels must be completed entirely with the necessary information and recorded in the IP Accountability Log at the investigational site. In the event of an emergency, the contents of the kit can be unblinded using the proper procedures as outlined in the protocol (see [Section 15](#)) and by instructions provided to the site.

A 3.2 Investigational Product Storage and Preparation

IPs will be stored under secure conditions until they are dispensed to the subjects. IPs should be stored in accordance with the temperature specified on the label.

A 3.3 Dispensing Investigational Product

Sites will receive shipments of IP kits from the Sponsor or designee. Subjects who are eligible for enrollment into the study will be randomized using the IWRS and dispensed the kit numbers assigned by the IWRS. Subjects will be dispensed two kits each containing 20 unit dose droppers of the IP on a monthly basis for the duration of the treatment phase. In the event that the “use by” date of the IP will be reached prior to the next scheduled visit, subjects should contact the study site to arrange for a fresh supply.

The IP must be dispensed only to study subjects and only at study sites specified on the signed ‘Statement of Investigator’ (e.g., Form FDA 1572 or equivalent) required by applicable regulations and guidelines.

Each unit dose dropper will deliver ~1 mL per application and will be provided to the subject in a storage container.

Information will be recorded on the IP Accountability Log. Prior to dispensing to the subject, the total group of unit dose droppers will be weighed. The subjects will be instructed to bring all droppers of the IP (used and unused) to each clinic visit.

At each post-Baseline visit, site staff will collect all droppers (used and unused) of the IP and record the necessary information in the IP Accountability Log. Site staff will review the IP application procedure and subjects will be counseled on IP compliance, as necessary. Any

discrepancies or concerns with the subject regarding the use of the Subject Diary to record IP applications should be addressed. At the end of subject's participation in the treatment phase, the total group of returned unit dose droppers will be weighed.

A 3.4 Investigational Product Supply Records at Study Sites

It is the responsibility of the investigator to ensure that a current record of IP disposition is maintained. Records or logs must comply with applicable regulations and guidelines, and should include:

- Amount received placed in storage area.
- Amount currently in storage area.
- Label ID number or batch number.
- Dates and initials of the person responsible for each product inventory entry/movement.
- Amount (number and units and weights) dispensed to and returned by each subject, including unique subject identifiers.
- Amount transferred to another area for dispensing or storage.
- Non-study disposition (e.g., lost, wasted, broken).
- Amount returned to Sponsor.
- Amount destroyed at study site, if applicable.

TI will provide forms to facilitate inventory control if the staff at the study site does not have an established system that meets these requirements.

A 3.5 Dose Modifications

The subject should not modify the treatment regimen without consultation with the Investigator. Subjects should be instructed to discontinue use if skin irritation or rash develops and to contact the study site immediately. In the event that the Investigator believes that dose modification is necessary (e.g., problems with tolerance), the subject's care should be discussed with the Medical Monitor prior to making any dose modifications. All dose modifications must be reported on the appropriate eCRF.

A 3.6 Documentation of Application and Compliance

The date of the first and last application of the IP will be recorded on the appropriate eCRF. Dosing times relative to PK blood draws will also be collected in the appropriate eCRF. An eCRF will also be used to record any changes from the application specified in the protocol (e.g., investigator directed reduction in application frequency or drug holiday).

A Subject Diary will be dispensed to subjects to record the dates and times of all applications and to record any missed doses of the IP ([Appendix 2](#)). Subjects will be instructed to bring the Subject Diary with them to each study visit.

A 3.7 Return and Destruction of Investigational Product Supplies

Upon completion or termination of the study, all remaining IP containers must be a) returned to the Sponsor or designee by a traceable method for final accountability and destruction or b) appropriately destroyed in accordance with applicable regulations with the provision of a certificate of destruction. All missing containers of IP must be explained on the completed IP Accountability Log. A copy of the IP Accountability Log and Label Pages (if applicable) will be returned to the Sponsor or designee. Upon receipt of the IP, a Sponsor representative will perform a final reconciliation. TI will be notified of any missing IP.

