6.3 Warnings, Precautions, and Contraindications

The IPs are for topical use on the scalp only and for use by men only. The IP should not be applied to other parts of the body. Care should be taken to minimize inadvertent transfer of the IP to close contacts.

Care should be taken to avoid contact with eyes and all mucous membranes. If contact with eyes occurs, rinse thoroughly with water. If inadvertent transfer of the IP occurs with a close contact, such area of contact should be washed with soap and water as soon as possible.

Subjects with a known sensitivity to any of the ingredients in the IPs should not participate in this study.

Should skin irritation or rash develop, the subject should be instructed to contact the site immediately.

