- Perform the scalp micro-dot tattoo procedure ([Section 11.2](#)) if it has significantly faded.
- Perform standardized macro photography ([Section 11.2](#)).
- Have subject complete the SSA questionnaires for scalp hair growth using the standardized global photos of the subject's scalp taken at Visit 1/Screening and comparing it to the current visit's photos ([Section 10.3](#)).
- Complete the IGA for scalp hair growth using the standardized global photos of the subject's scalp taken at Visit 1/Screening and comparing it to the current visit's photos ([Section 10.2](#)).
- Record LSRs ([Section 10.4.4](#)).
- Collect PK blood sample 1 to 4 hours after IP application ([Section 12.5](#)).
- Allocate new IP kit numbers using the IWRS and dispense the corresponding kits. Record IP Accountability.
- Collect, review, and dispense a new Subject Diary, as needed.
- Document any AEs.
- Schedule the next visit.

9.5 Visit 5 (Day 42 ± 3) and Visit 7 (Day 70 ± 3): Weeks 6 and 10 Phone Call

At this visit, the investigator or designee will:

- Contact the subject by telephone and query the subject for any changes in health status and document the findings.
- Remind the subject to continue to apply the IP every morning until the next clinic visit and to record all applications in the Subject Diary.
- Discuss any AEs with the investigator to determine if the subject should return to the study site for an unscheduled visit.
- Confirm the next visit.

9.6 Visit 8 (Day 84 ± 3) and Visit 9 (Day 112 ± 3): Weeks 12 and 16/End of Treatment

Note: Visits should be scheduled so that PK sample collection will occur 1 to 4 hours after the subject has self-applied the IP application at home.

At this visit, the investigator or designee will:

- Query the subject for any changes in health status since the previous visit, including concomitant medications and concurrent procedures/therapies, and document the findings.
- Perform a physical examination ([Section 10.4.1](#)).
- Measure vital signs ([Section 10.4.2](#)) with height and weight at Visit 9 only.
- Perform 12-lead ECG ([Section 10.4.3](#)).

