APPENDIX 1 SAMPLE SUBJECT INSTRUCTION SHEET

Copies of the following sample subject instructions will be provided to the study site. The investigator must give each subject a copy of this instruction sheet at Visit 2/Baseline prior to dispensing the IP.

**SAMPLE SUBJECT INSTRUCTION SHEET
PROTOCOL 239-11651-203**

Please follow these instructions carefully. Contact the study staff at the telephone number noted below if you have any questions about the study:

Contact: _____ At: _____

Please apply the study medication to the balding areas of your scalp
ONCE DAILY at approximately the same time as Day 1 application every morning.

STUDY MEDICATION APPLICATION INSTRUCTIONS:

1. Wash the scalp with your typical shampoo and dry the hair each morning before your daily study medication application.
2. For those days when you have a clinic visit, remember to bring your study medication supplies with you to the clinic.
3. Wash and dry your hands thoroughly.
4. Apply 1 mL of the study medication to the balding and thinning areas of your scalp using the provided dropper (see directions below on using the dropper).
5. Spread the solution evenly over the hair loss area and **gently massage** the solution into the scalp with an emphasis over the entire balding area and adjacent regions with thinning hair. It may be helpful to apply the study medication in front of a mirror.
6. Wash and dry your hands thoroughly after application.
7. Record the date and time of study medication application in your Subject Diary. If the full 1 mL was applied, check YES box indicating that the full dose was applied. If the full 1 mL dose was not applied, check NO and include an explanation as to why the full dose was not applied.
8. If you miss a dose, record MISSED in your Subject Diary and then, apply the next dose at the regular time. Apply the dose at approximately the same time every morning.
9. Continue use of the study medication unless directed otherwise by the study doctor. Contact the study staff or study doctor at the number above if you have questions or before stopping use of the study medication for any reason.

USING THE DROPPER APPLICATOR:

1. Each unit dose dropper contains enough study medication to dispense approximately 1 ml of solution.
2. Remove the cap.
3. Invert the dropper with the tip side down over the area of the scalp to be treated.
4. Study medication may be applied as a:

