 - i) Grouping of Single Drops - which may be dispensed by holding the dropper over the affected area of the scalp and as necessary gently squeezing the unit dose dropper, and/or

ii) Single Line of Solution – which may be applied by (i) parting the thinning hair (or use an imaginary line on the bald scalp), (ii) place the dropper tip on to the scalp surface at the top of the part, (iii) keeping the tip in contact with the scalp along the part as you gently squeeze the unit dose dropper while you advance the dropper along the entire part line.

NOTE: apply only a few drops or a fine line of solution, one at a time, to avoid having the study medication drip off your scalp then proceed to Step #5

5. After applying the study medication, spread the solution evenly over the hair loss area and gently massage the solution into the scalp.
6. Repeat steps 4 and 5 focusing on all bald and thinning scalp areas not treated with the solution until all areas of balding are treated AND the entire content of the unit dropper is used.

REMINDERS:

- Only apply the study medication as directed by the study doctor.
- **Do not wash the treated area, bathe, shower, swim, or have exposure to water for at least approximately 4 hours following application of the study medication.**
- **Avoid rigorous exercise for at least approximately 4 hours following application of the study medication.**
- **Avoid wearing a cap or hat within at least approximately 30 minutes following application of the study medication.**
- **General hair care products and regimen must be continued for the entire study.**
- Store the study medication according to the instructions on the label.
- Bring all containers of the study medication (used and unused) and the completed Subject Diary to each visit.
- Do not allow anyone else to use the study medications: keep containers of study medication away from children/pets. Avoid inadvertent transfer of the study medication to close contacts.
- If skin irritation develops, contact the study site immediately.
- Avoid contact with eyes and all mucous membranes. If contact with eyes occurs, rinse thoroughly with water. If inadvertent transfer of the study medication occurs with a close contact, such areas of contact should be washed with soap and water as soon as possible.

STUDY VISIT SCHEDULE:

Visit 3	Visit 4	Visit 5 Phone	Visit 6	Visit 7 Phone	Visit 8	Visit 9	Visit 10

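### The instruction sheet given to every subject omits the protocol's instruction to stop the product if skin irritation or rash develops, and its item 9 contradicts that instruction

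*Protocol*

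**What the plan says.** Four places in the protocol bear on what a subject should do when the scalp becomes irritated.

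- **Appendix 3, A 3.5 (Dose Modifications)** opens with a general rule: "The subject should not modify the treatment regimen without consultation with the Investigator". The next sentence is specific: "Subjects should be instructed to discontinue use if skin irritation or rash develops and to contact the study site immediately".
- **Appendix 1, item 9 of the Subject Instruction Sheet** says: "Continue use of the study medication unless directed otherwise by the study doctor". It then asks the subject to contact the study staff or study doctor with questions, or "before stopping use of the study medication for any reason".
- **Appendix 1, Reminders** on the same sheet: "If skin irritation develops, contact the study site immediately".
- **Section 6.3 (Warnings, Precautions, and Contraindications)**: "Should skin irritation or rash develop, the subject should be instructed to contact the site immediately".

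The introduction to Appendix 1 fixes the status of the sheet: "The investigator must give each subject a copy of this instruction sheet at Visit 2/Baseline prior to dispensing the IP".

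**The concern.** A 3.5 makes stopping the default response to irritation or rash, with contact alongside it. Item 9 makes continuing the default and puts contact ahead of any stop. The two differ in what the subject does between noticing a reaction and hearing from the site. A 3.5 has him off the product in that interval; the sheet has him on it.

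The sheet is the written instruction the subject takes home. A 3.5 sits in an appendix on product supply, addressed to sites. If the two disagree, the subject is likely to act on the one in his hands. At stake is a local safety measure in a study that lists safety and tolerability among its objectives.

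**Working it through.** There is no figure in the plan to reproduce, and no calculation applies. The check is a comparison of the texts on three questions.

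| Place | Stop on irritation or rash? | Contact the site? | Rash named? |
|---|---|---|---|
| A 3.5, second sentence | Yes | Yes, immediately | Yes |
| Instruction Sheet, item 9 | No; continue unless directed otherwise | Yes, before stopping | Neither irritation nor rash is named |
| Instruction Sheet, Reminders | Silent | Yes, immediately | No, irritation only |
| Section 6.3 | Silent | Yes, immediately | Yes |

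**Step 1: omission or conflict?** The Reminders and Section 6.3 are incomplete next to A 3.5, but a subject could obey them and A 3.5 together. Item 9 is different. It covers stopping for any reason and contains no exception, so irritation and rash fall within it. Under A 3.5 the subject may stop first; under item 9 he may not. Both cannot be followed as written.

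**Step 2: does A 3.5 settle the matter itself?** Its first sentence forbids changes without consultation and its second tells the subject to stop. The usual reading is that the specific sentence qualifies the general one. A 3.5 does not say so, however, and item 9 has in effect carried over the first sentence without the second.

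**Step 3: does the stop instruction reach the subject in writing elsewhere?** Not in the sheet, and Section 6.3 does not ask sites to give it. Among the texts compared, it stands only in A 3.5.

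**Step 4: what is the consequence?** It depends on how quickly the subject reaches the site. Dosing is once daily. If he calls and is answered before the next morning's dose, there may be no further application. If not, item 9 has him apply again. The documents give neither a response time nor an irritation rate for this study, so the size of the effect cannot be calculated from them.

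**The case against.** The strongest reply is that the gap is narrow. The sheet agrees with the first sentence of A 3.5 and with Section 6.3; what it lacks is one clause and the word rash. It tells the subject to make contact immediately and has a space for a contact number. It is labelled a sample. A 3.5 does not say that the stop instruction must be given through the sheet: Section 9.2 provides for instruction in person at Baseline, and Appendix 3 has staff review the application procedure at each post-Baseline visit. Earlier experience is also reassuring: the single-dose study recorded no local skin reactions, and the doses in the four-week study were well tolerated.

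Most of this stands and limits the harm. It does not remove the conflict. Spoken advice that contradicts the paper the subject keeps is a weak safeguard, and the sample text should match the rule it serves.

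Four stronger readings are tempting, and the documents do not support them.

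- *That subjects never receive the stop instruction.* Sites may give it orally, and the consent form is not among the documents reviewed. The text shows an inconsistency, not a failure of delivery.
- *That the Week 6 and Week 10 calls push subjects to treat through a reaction.* Section 9.5 does tell staff: "Remind the subject to continue to apply the IP every morning until the next clinic visit". But the same call asks about changes in health status and takes adverse events to the investigator. It is an adherence reminder within a safety contact.
- *That the extra exposure can be expressed as a dose.* That would need an assumed delay, which may be zero, and nothing in the documents links the amount of active drug to irritation.
- *That the rule making the six listed skin reactions adverse events only when they need medical intervention should be widened to cover stopping the product.* Those reactions are graded and tabulated separately, including at early termination, and dose modifications go on their own form. With a stop-on-irritation instruction in place, the wider trigger would turn a minimal reaction noticed at home into an adverse event. That is a debatable trade-off, not an error.

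**Conclusion.** The point holds, and it is minor. The protocol gives a stop instruction for irritation or rash in A 3.5. The sheet that every subject must receive omits it, and item 9 of that sheet contradicts it. The Reminders and Section 6.3 mention contact alone, and the Reminders leave out rash.

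The consequence is confined to the interval between onset of a reaction and the site's advice, and the instruction to contact the site immediately should keep that interval short. No count of affected subjects is claimed. The efficacy endpoints and their analyses do not depend on this point. The conclusion assumes that A 3.5 states what the sponsor intends. If the sponsor instead wants subjects to keep applying until advised, A 3.5 is the text to change; the inconsistency still needs resolving.

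**What to change.** Taking A 3.5 as the intended rule:

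1. In item 9 of the Instruction Sheet, add: *Exception: if skin irritation or rash develops, stop use and contact the study site immediately.*
2. Use the same wording in the sheet's Reminders, which adds rash there, and in Section 6.3.
3. In A 3.5, state that this is the exception to the rule against changing the regimen without consultation.

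The cost is a wording amendment to the protocol and the sheet, with IRB approval. No visit, assessment or analysis changes. The downside is that A 3.5 sets no severity grade, so some subjects may miss doses for a minimal reaction until the site advises. Short pauses need not change how a subject is classed for compliance. Once-daily dosing for 16 weeks is 16 × 7 = 112 applications, and 80% of 112 is 89.6. A subject with 90 applications would still meet the 80% threshold, which allows 112 − 90 = 22 missed doses if he has no other material non-compliance.

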1. INTRODUCTION

This Statistical Analysis Plan (SAP) describes the planned statistical analyses to be performed for data from Protocol 239-11651-203, A Randomized, Double-Blind, Vehicle-Controlled, Parallel Group, Multi-Dose Study to Evaluate the Efficacy and Safety of TDM-105795 in Male Subjects with Androgenetic Alopecia.

This SAP was created using Clinical Protocol 239-11651-203 Version 1.0 dated November 30, 2022, and the Electronic Case Report Forms (eCRF) Version 1.0 dated March 08, 2023.

2. PURPOSE OF THE ANALYSES

The purpose of this SAP is to outline the planned analyses to be completed to support the Clinical Study Report (CSR) for Protocol 239-11651-203. Any post-hoc or unplanned analyses not identified in this SAP will be clearly identified in the CSR.

3. STUDY OBJECTIVES AND ENDPOINTS

3.1 Objectives

1. To evaluate efficacy of TDM-105795 administered topically in male subjects with androgenetic alopecia (AGA).
2. To evaluate the safety and tolerability of TDM-105795 administered topically in male subjects with AGA.
3. To evaluate the pharmacokinetics (PK)/pharmacodynamics (PD) of TDM-105795.

